Appendix B 5 Committees Structure	Rapidly Progressive Osteoarthritis AdjudicationCommitteeThe role of the Rapidly Progressive OsteoarthritisAdjudication Committee (RPOA-AC) is toindependently review, interpret, and adjudicatepossible or probable joint safety events including butnot limited to RPOA, subchondral insufficiencyfracture, primary osteonecrosis, or pathologicalfracture cases that are experienced by the studyparticipants. The adjudication committee will reviewall cases of suspected joint safety events todetermine whether or not they meet accepteddiagnostic criteria. The RPOA-AC will review andadjudicate all joint safety events that meet SAE orsevere AE criteria or AEs that led to jointreplacement or other arthroplasty procedures. Jointsafety events will be identified preliminarily by the	Rapidly Progressive Osteoarthritis AdjudicationCommitteeThe role of the Rapidly Progressive OsteoarthritisAdjudication Committee (RPOA-AC) is toindependently review, interpret, and adjudicatepossible or probable joint safety events including butnot limited to RPOA, subchondral insufficiencyfracture, primary osteonecrosis, or pathological fracturecases that are experienced by the study participants.The adjudication committee will review all cases ofsuspected joint safety events to determine whether ornot they meet accepted diagnostic criteria.The RPOA-AC will review and adjudicate all joint safety eventsthat meet SAE or severe AE criteria or AEs that led tojoint replacement or other arthroplasty procedures todetermine whether or not they meet accepteddiagnostic criteria.Joint safety events will be identified	Redundant sentence removed as joint safety events that will be reviewed by RPOA-AC are specified: RPOA, subchondral insufficiency fracture, primary osteonecrosis, or pathological fracture and all joint safety events that meet SAE or severe AE criteria or AEs that led to joint replacement or other arthroplasty procedures	Non- substantial	

Section # and Name	Initia	l Wording und	er Version 1	Amended or	New Wording un	Brief Rationale	Substantial/ Non- substantial
	personnel or du	nd also by Astra uring the RPOA- e committee's ch	AC process as	AstraZeneca/spo	the investigators, onsor personnel or pecified in the com		
Appendix B 10 Publication Policy	presented at sc must agree to s the sponsor bet	ubmit all manus fore submission. ect proprietary in	. The investigator cripts or abstracts to	at scientific mee managed by the sponsor for revie The investigator or abstracts to the allows the spons accuracy and to	is study may be pu tings. Publications investigator will b ew and approval be must agree to sub the sponsor before s sor to review the pu ensure protect any rotected. and to pro-	Revised in response to German Ethics Committee (EC) query as to clarify that the purpose of the publication policy is to identify and remove any proprietary information from the publication	Non- substantial
Appendix I Summary of	Imaging Ass During the S	essments to be l Study	Performed	Imaging Asses the Study	ssments to be Per	To clarify that MRI of shoulder joints will be performed only when deemed necessary based on central reader evaluation of X-ray data and when it is clinically indicated during the study (due to issues with accurate definition of KL grade 3 in shoulder joints)	Non- substantial
Imaging Assessments	Joints/ X-ray (plain MRI indications radio-	MRI	Joints/ indications	X-ray (plain radiographs)	MRI		
(Table I11)	Shoulders (both)	graphs E and S	for joints with KL grade 3 or more	Shoulders (both)	j		

Section # and Name	Initial Wording under Version 1					Amendeo	l or New Wol	rding under A	Brief Rationale	Substantial/ Non- substantial	
Appendix I	Schedule of Assessments - Imaging					Schedule	of Assessmen	ts - Imaging	To clarify that MRI of	Non-	
Summary of	Imaging	Knee	Hip	Shoulder	1 [Imaging	Knee	Hip	Shoulder	shoulder joints will be	substantial
Imaging Assessments (Table I12)	MRI	Both knee joints at screening and as clinically indicated during the study	Joints with KL grade 3 or more at screening and as clinically indicated during the study	For joints with KL grade 3 or more at screening and as clinically indicated during the study		MRI	Both knee joints at screening and as clinically indicated during the study	Joints with KL grade 3 or more at screening and as clinically indicated during the study	For joints with KL grade 3 or more at screening and As clinically indicated during the study	performed only when clinically indicated during the study	

Abbreviations are found in Appendix L.

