After the end-of-treatment (EOT) visit at Week 12, participants will enter the FU period, which comprises 3 clinic visits (Weeks 18, 32, and 36) and 4 FU phone calls (Weeks 15, 21, 24, and 28). All participants who receive IP are expected to complete the FU period.

Interim Analysis

The study incorporates 2 interim analyses: (1) a futility analysis will take place when approximately 25% of participants are evaluable for the primary endpoint; this analysis will assess the likely success of the study outcome and will enable the sponsor to make a go/no-go decision regarding continuation of the study; and (2) an interim analysis of efficacy data will take place when approximately 50% of participants are evaluable for the primary endpoint; this analysis will enable the sponsor to plan future project-related activities, but without making any changes to the current study.

No alpha adjustment is required for the interim analyses because early stopping for efficacy is not a feature of the study design.

Disclosure Statement

This is a Phase IIb, randomised, parallel-group, placebo-controlled, double-blind treatment study of MEDI7352 with 5 cohorts that are participant- and investigator-blinded.

Number of Subjects

This is a multinational, multicentre, interventional study in which approximately 350 eligible participants will be randomly assigned to the IPs (one of 4 dose levels of MEDI7352 or placebo).

Intervention Groups and Duration

Screening period: up to 45 days

Randomisation: participants will be randomised in a ratio of 1:1:1:1:1, respectively, to one of the following 5 treatment cohorts:

- ∀ Cohort 1: CCI MEDI7352 Q2W administered CC
- ∀ Cohort 2: CCI MEDI7352 Q2W administered CC
- ∀ Cohort 3: CCI MEDI7352 Q2W administered CC
- ∀ Cohort 4: CCI MEDI7352 Q2W administered
- ∀ Cohort 5: Placebo to match MEDI7352 Q2W administered ^{CC}

Treatment period: 12 weeks with 6 fixed doses of IP administered at Weeks 0 (Day 1), 2, 4, 6, 8, and 10 and an EOT visit conducted at Week 12

FU period: 24-week FU period with a final FU visit at Week 36 (\pm 7 days)

The maximum study duration for each participant is approximately 50 weeks. The overall study duration is expected to be 31 months (18 months of active screening and enrolment, 11 months of treatment and FU, and 2 months for database lock).

Data Monitoring Committees:

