6.6 Dose Modification

Dose adjustment is not allowed in this study. Participants will be allocated to a single dosing regimen at randomisation.

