7.1.1 Subject-specific Criteria for Discontinuation of Investigational Product

For any individual participant, further administration of IP will be stopped if any of the following scenarios occur:

- # Reports of drug-related SAE(s) or drug-related AE(s) including but not necessarily limited to:
 - Serious or severe drug-related injection site reactions
 - Anaphylactic reaction, defined as an immediately life-threatening allergic reaction with bronchoconstriction, angioedema, and/or hypotension (FDA 2014); or serious hypersensitivity reactions
 - Development of moderate-to-severe sensory abnormalities (eg, paraesthesia, dysesthesia, burning, pins and needles) that are not resolved within a 14-day period
 - Development of peripheral neuropathy
 - New onset of demyelinating disorder
 - Serious systemic infection
 - o Serious non-systemic infection if deemed necessary by the investigator

- # Any of the following are criteria for immediate and permanent discontinuation of IP (Section 8.2.11.1):
 - \circ ALT or AST > 5 × ULN for more than 2 weeks
 - ALT or AST ≥ 3 × ULN and coexisting total bilirubin ≥ 2 × ULN (Hy's Law [HL]). Hy's law is described in Section 8.3.8 and FU of HL cases is provided in Appendix F.
 - \circ ALT or AST \geq 3 × ULN and coexisting international normalised ratio (INR) > 1.5
 - ALT or AST ≥ 3 × ULN and associated with symptoms (which may be either transient or persistent) of hepatitis or hypersensitivity. Hepatitis symptoms include fatigue, nausea, vomiting, right upper quadrant pain or tenderness. Hypersensitivity symptoms include eosinophilia (≥ 5%), rash, or fever without clear alternative cause.
 - Any change in ALT or AST level (eg, < 3 × ULN) if there is a possibility of development of autoimmune hepatitis as per investigator's judgement. Participant should have a consult with a hepatologist, and liver chemistry values, as well as additional tests, should be completed as soon as possible (Appendix F 7)
- # AEs suggestive of autonomous nervous system dysfunction, including but not limited to confirmed orthostatic hypotension (Section 8.2.3.2) or significant bradycardia (Section 8.2.4) or syncope that after evaluation by a cardiologist (and/or neurologist) are considered to be a manifestation of sympathetic autonomic dysfunction
- # Cases when sympathetic neuropathy is not confirmed but orthostatic hypotension remains symptomatic for more than 14 days

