- # Participants who have a proven diagnosis of sympathetic autonomic neuropathy
- # Development of malignancy
- # Development of Class 3 or Class 4 (NYHA 1994) heart failure
- # Positively-adjudicated possible or probable RPOA, SIF, primary osteonecrosis (including spontaneous osteonecrosis of the knee), or pathological fracture.
- # Participants who plan to undergo total joint replacement (knee, hip, or shoulder) or other arthroplasty procedure during the study
- # Haematologic toxicity, defined as one or more of the following:*
 - Leukocyte count $< 2.0 \times 10^9/L$
 - \circ Neutrophil count $< 1.0 \times 10^{9}/L$
 - \circ Platelet count < 75 × 10⁹/L
 - * Note: Participants must be advised to seek immediate medical attention if they develop any symptoms suggestive of blood dyscrasia or infection (eg,

persistent fever, sore throat, bruising, bleeding, or pallor). Haematology testing should be performed as soon as possible to exclude blood dyscrasia.

- # Development of a lupus-like syndrome, autoimmune hepatitis, or immune-complex disease
- # Development of COVID-19 infection that meets moderate or severe severity AE criteria.
- # Treatment with anti-SARS-CoV-2 monoclonal antibodies for COVID-19 infection of any severity.
- # Mild or asymptomatic COVID-19 infection with symptoms that have not resolved within 28 days since the last IP administration or results of appropriate testing for COVID-19 infection (ie, antigen-based) suggesting that a participant is carrying a replicating virus and remains positive within 28 days since the last IP administration.
- # There are other ongoing sequelae from COVID-19 infection, or the participant requires treatment for the manifestations of COVID-19 infection for the period beyond 28 days since the previous IP administration, or less than 5 half-lives have passed since the last COVID-19 antiviral medications administration within the 28-day period since the last IP administration.
- # If per investigator's judgement, the amount of rescue medication taken by the participant poses a risk for the participant to continue safely in the study.

7.1.2 **Procedures for Early Discontinuation of Investigational Product**

A participant who discontinues IP early (ie, prior to receiving the last dose of IP) should always be asked about the reason(s) and the presence of any AEs. The reason for premature discontinuation of IP should be documented in the source documentation and recorded in the eCRF.

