8.2.9 Injection Site Reactions

Investigators should evaluate injection site reactions that occur during or immediately following IP administration per the FDA Guidance for Industry, Immunogenicity Assessment for Therapeutic Protein Products (FDA 2014) and FDA Guidance for Industry, Toxicity Grading Scale for Healthy Adult and Adolescent Volunteers Enrolled in Preventive Vaccine Clinical Trials (FDA 2007). See Section 2.3 for potential risks related to injection site reactions.

Investigators should evaluate injection site reactions using the toxicity grading scale summarised in Table 7.

Local Reaction	Mild	Moderate	Severe ^a
Pain	Does not interfere with activity	Repeated use of non-narcotic pain reliever > 24 hours or interferes with activity	Any use of narcotic pain reliever or prevents daily activity
Tenderness	Mild discomfort to touch	Discomfort with movement	Significant discomfort at rest
Erythema/redness ^b	2.5 to 5 cm	5.1 to 10 cm	> 10 cm
Induration/swelling ^c	2.5 to 5 cm and does not interfere with activity	5.1 to 10 cm or interferes with activity	> 10 cm or prevents daily activity

Table 7Local Reaction to Injectable Product

^a In addition, the reactions in which ulceration or severe necrosis occurs should be considered as severe as per CTCAE v5.

^b In addition to grading the measured local reaction at the greatest single diameter, the measurement should be recorded as a continuous variable.

^c Induration/swelling should be evaluated and graded using the functional scale as well as the actual measurement.

CTCAE, common terminology criteria for adverse events

Source: FDA 2007

Injection site reactions will be monitored at the study visits indicated in the SoA (Table 1). On Day 1, injection site reactions will be monitored at approximately 5, 15, 30, 45, and 60 minutes and 2 and 4 hours after completion of IP administration. On other dosing days, injection site reactions will be monitored per standard process of AE collection (participants will be instructed to report any changes occurred at the injection site).

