8.3.1 Time Period and Frequency for Collecting AE and SAE Information

Adverse events will be collected from Visit 1 (including AEs related to washout period at screening), throughout the study, and including the FU period (last contact with participant).

Serious AEs will be recorded from the time the participant signs the ICF and throughout the study. All SAEs and AESIs will be recorded and reported to AstraZeneca or designee within 24 hours of awareness, as indicated in Appendix C. The investigator will submit any updated SAE data to AstraZeneca within 24 hours of it being available.

If the investigator becomes aware of an SAE with a suspected causal relationship to the investigational medicinal product that occurs after the end of the clinical study in a participant treated by him or her, the investigator shall, without undue delay, report the SAE to the AstraZeneca.

The method of recording, evaluating, and assessing causality of AE and SAE and the procedures for completing and transmitting SAE reports are provided in Appendix C.

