8.3.5 Adverse Events of Special Interest

An AESI is a treatment-emergent AE of scientific and medical interest specific to understanding of the effects of the IP and may require close monitoring and collection of additional information by the investigator. An AESI may be serious or nonserious. The rapid reporting of AESIs allows ongoing surveillance of these events in order to characterise and understand them in association with the use of MEDI7352.

Refer to Section 2.3.1 for a summary of potential risks and the IB for a detailed discussion of potential risks.

The following AESIs have been identified specifically for this MEDI7352 protocol and are to be reported as described in Section 8.3.1 through Section 8.3.4:

- ∀ Positively-adjudicated possible or probable RPOA, SIF, primary osteonecrosis, or pathological fracture
- ∀ Infections that meet SAE or severe AE criteria*
- ∀ Anaphylactic reactions; serious or severe hypersensitivity reactions; or injection site reactions that lead to permanent discontinuation of administration of IP

Adverse events of special interest irrespective of their severity and seriousness should be reported immediately using the same procedure as for SAE reporting (Section 8.3.9).

*Note: A serious infection is any infection that meets the SAE criteria in CSP Appendix C 2 "Definition of Serious Adverse Event." Serious infection AEs should be reported as SAEs. A severe infection is any infection that does not meet SAE criteria but is incapacitating, with inability to perform normal activities. Non-serious severe infections are reported as AEs. It is expected that microorganism culture results and all diagnostic or therapeutic procedure results performed on a study participant experiencing a serious or severe infection will be provided as an SAE/AESI update.

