8.2.10 Procedures for Subjects Undergoing Joint Replacement	AEs that led to joint replacement surgery should be followed up by the investigator for as long as medically indicated but no less than up to the end of the FU period.	AEs that led to joint replacement surgery should be followed up by the investigator for as long as medically indicated but no less than up to the end of the FU period or 4 months since joint replacement surgery (whichever is longer). Data on additional or corrective procedures (for example a revision or implant replacement) that were necessary after total joint replacement and their outcomes should be collected wherever possible as well.	The minimal duration of FU period to assess joint replacement surgery outcomes and additional information that is expected to be collected in joint replacement surgery cases is added	Substantial
8.2.11.3 Urine Drug Screen	The urine drug test will be performed only at screening (Table 1).	The urine drug test will be performed at the time points shown in only at screening (Table 1).	To clarify time points in the text and correct discrepancy with Table 1	Non- substantial
8.3.5 Adverse Events of Special Interest	The following AESIs have been identified specifically for this MEDI7352 protocol and are to be reported as described in Section 8.3.1 through Section 8.3.4.	The following AESIs have been identified specifically for this MEDI7352 protocol and are to be reported as described in Section 8.3.1 through Section 8.3.4. •	Additional events have been added to AESIs for safety data collection and monitoring purposes	Substantial

Section # and Name	Initial Wording under Amendment 1	Amended or New Wording under Amendment 2 (Deletions are strikethrough, and additions are underlined)	Brief Rationale	Substantial/ Non-substantial
	 Anaphylactic reactions and injection site reactions that lead to discontinuation of administration of IP 	Anaphylactic reactions ; serious or severe hypersensitivity reactions; or and injection site reactions that lead to permanent discontinuation of administration of IP		
CCI				Non- substantial
8.6.1.1 Pharmacodynamic Biomarkers	Results from the PD biomarker analyses will be reported in the CSR.	Results from the PD biomarker analyses may will be presented separately from the CSR.	For consistency with Section 9.4.4.2.	Non- substantial
CCI				Non- substantial
				Non- substantial

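### A severe, non-serious, drug-related injection site reaction is an AESI after doses 1 to 5 but cannot be one after dose 6, because Section 8.3.5 ties AESI status to stopping IP

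*Protocol*

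**What the plan says.** The relevant AESI bullet in Section 8.3.5 reads "Anaphylactic reactions; serious or severe hypersensitivity reactions; or injection site reactions that lead to permanent discontinuation of administration of IP". The Amendment 2 entry in Appendix M shows the same condition, "injection site reactions that lead to permanent discontinuation of administration of IP", as its new wording, so this is the rule in force.

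The provisions that interact with it are:

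- **Dosing (Section 1.1).** The treatment period is "12 weeks with 6 fixed doses of IP administered at Weeks 0 (Day 1), 2, 4, 6, 8, and 10". Section 6.6 adds: "Dose adjustment is not allowed in this study".
- **Stopping (Section 7.1.1).** Further IP is stopped for events that include "Serious or severe drug-related injection site reactions".
- **Meaning of early discontinuation (Section 7.1.2).** The section describes "A participant who discontinues IP early (ie, prior to receiving the last dose of IP", so the term applies only while a dose is still due.
- **Reporting (Section 8.3.1).** "All SAEs and AESIs will be recorded and reported to AstraZeneca or designee within 24 hours of awareness".
- **Collection (Section 8.2.9).** Reactions are graded with Table 7. Day 1 has scheduled checks. After that, "On other dosing days, injection site reactions will be monitored per standard process of AE collection".
- **Presentation.** Section 9.4.3.1 plans separate AE tables by severity, by relationship, for SAEs and for AESIs, with AESI listings. Section 9.4.3.6 has injection site reaction findings listed, and summarised only if warranted.

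**The concern.** The other two AESI bullets in Section 8.3.5 are defined by the event itself: adjudicated joint events, and infections that are serious or severe. For injection site reactions the definition turns on what was done with IP. That works as a proxy for severity only while there is IP left to stop.

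At the last dose the proxy fails. Two participants with the same severe, non-serious, drug-related reaction are classified differently because one had a dose still to come and the other did not. What is at stake is whether the AESI tables cover all six doses on the same basis, and whether the sponsor hears of such a reaction within 24 hours. Efficacy, the estimand and the testing strategy are not involved.

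**Working it through.** **Inputs from the protocol**

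- Dosing weeks: 0, 2, 4, 6, 8, 10 (Section 1.1). The count is 6, which reproduces the stated number of doses, and none follows Week 10.
- Planned randomised number: about 350 (Section 9.2).
- Criterion that stops IP for a local reaction: serious or severe and drug-related (Section 7.1.1).

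**Step 1: follow one reaction through the rules.** Take a severe, non-serious, drug-related injection site reaction.

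| | After doses 1 to 5 | After dose 6 |
|---|---|---|
| Section 7.1.1 | IP must stop | No further IP to stop |
| Section 7.1.2 early discontinuation | Yes, a dose was still due | No, the last dose was received |
| AESI under Section 8.3.5 | Yes | No |
| 24-hour report under Section 8.3.1 | Yes, as an AESI | No: neither AESI nor SAE |
| AE record, Table 7 grade, AE tables, listing | Yes | Yes |

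If the reaction is serious, the 24-hour row reads yes in both columns, because it is an SAE. After dose 6 it then loses only the AESI label.

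**Step 2: share of dosing occasions affected, full dosing.** Planned occasions are 350 × 6 = 2100, of which 350 are dose 6. The share is 350/2100 = 1/6 = 16.7%. The definition can operate on 350 × 5 = 1750 occasions.

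**Step 3: share with dropout (assumed).** Let c be the fraction reaching dose 6, with constant retention q = c^(1/5) from one dose to the next. The share is q⁵ / (1 + q + q² + q³ + q⁴ + q⁵).

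- c = 0.85: about 1939 occasions in all. Dose 6 contributes 0.85 × 350 = 297.5, which is 15.3%.
- c = 255/350 = 0.729: about 1803 occasions. Dose 6 contributes 255, which is 14.1%.

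Both values of c are assumptions. The 255 in Section 9.2 is an information target, not a forecast of how many participants reach dose 6.

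**Step 4: number of events.** This cannot be derived, because the protocol gives no injection site reaction rate. For scale only, suppose a constant probability p per dose of a qualifying reaction and 280 participants on active drug (4/5 of 350), all dosed until a first such reaction. The expected number whose first one comes at dose 6 is 280 × p × (1 − p)⁵. That is 1.4 at p = 0.5% and 10.8 at p = 5%. Neither value of p comes from the documents, and both counts include serious reactions.

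**The case against.** The case for leaving the text alone is that little is lost and the choice was deliberate. Dose-6 reactions are collected, graded, tabulated by severity and relationship, and listed. Serious ones reach the sponsor within 24 hours as SAEs, and the DSMB reviews safety data throughout (Section 9.6). Amendment 2 inserted the word permanent, so the sponsor evidently wanted a category of treatment-ending local reactions. This stands as a limit on the size of the point. It does not explain why the same severe reaction should be classed differently according to whether a dose is still due.

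A reader might infer more than the documents support:

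- **That dose-6 reactions vanish from the safety data.** They do not, for the reasons just given. Only the AESI label is lost and, for severe non-serious reactions, the 24-hour report.
- **That anaphylaxis or severe hypersensitivity at dose 6 is also excluded.** The semicolons in Section 8.3.5 separate three items, and the discontinuation clause follows the last. Section 8.3.12 also defines anaphylaxis as a serious reaction, so it would be reported within 24 hours in any case. The wording merits a clarifying phrase, no more.
- **That dose 6 carries the highest risk because reactions build up.** Nothing in the protocol says so. The one infusion-related reaction it describes, with IV dosing, began at the second infusion (Section 2.2.2). The extended observation after Day 1 is at Visits 4 and 5, the second and third doses. The IV data do not settle local reaction risk either way.
- **That reported AESI rates are biased low.** That holds only against a different definition of the category.

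One theoretical exception exists. Each dose is two injections given no more than 2 minutes apart (Section 6.2.1), so a reaction to the first could in principle prevent the second. This hardly changes the conclusion.

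**Conclusion.** The inconsistency is real and minor. Read with Sections 1.1, 7.1.1 and 7.1.2, Section 8.3.5 makes a severe, non-serious, drug-related injection site reaction an AESI after doses 1 to 5 and excludes the same reaction after dose 6. The consequence is confined to AESI tabulation and the 24-hour report.

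The dose-6 exclusion follows from the text and needs no assumption about rates. The 16.7% share is of planned dosing occasions under full dosing, and the 14% to 15% figures depend on the assumed dropout pattern. Either figure is a share of events only if risk is equal at every dose. How many events are involved is unknown and could be none.

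**What to change.** Reconcile Section 8.3.5 with Section 7.1.1. Define this AESI as an injection site reaction that either leads to permanent discontinuation of IP, or meets the criterion already in Section 7.1.1 (serious or severe, and drug-related) after any dose, including the last. State in the same bullet that the discontinuation condition applies to injection site reactions only.

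The second limb would make all six dosing occasions eligible instead of five. A milder reaction over which the investigator stops IP would still qualify only while a dose is due. That is inherent in the first limb and can be left.

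The cost is one line of text and a few more 24-hour reports. Severity, seriousness and causality are already collected for every AE (Section 8.3.3) and Table 7 already supplies the grading, so no new data are needed. No dosing or stopping rule changes.
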